3.6. STOPPING RULES

Close safety monitoring is in place throughout the trial to ensure that safety issues of any form and severity will be identified early on and appropriately responded to as laid out elsewhere. IMPACT EDC engine automatically detects occurance of the stopping rules as defined in the study protocol. Once detected, the system will send automated notifications to prespecified team members. The stopping rules are defined as follows:

Stopping Rule 1: Subject Death

If at any time during the study, including roll-in/proficiency testing and enrollment, there are:

• one or more subject deaths reported to the sponsor,

the DMC will be informed within 24 hours and will perform an unblinded review. The DMC should make a determination by the end of the next business day after the event was reported to the sponsor.

If the DMC determines relatedness and decides that the safety profile of the study should be reconsidered, the study is put on hold immediately. Information of the event and DMC's decision is transmitted to FDA immediately. The study is not resumed unless and until FDA has decided that it is safe to do so.

If the DMC determines that the event is unrelated, or that the safety profile of the study remains unchanged, the study can be continued without interruption. In this case all information and the documentation of the DMC's decision is immediately brought to FDA's attention for further review at FDA's discretion.

Stopping Rule 2: Occurrence of Severe Hypotensive Events

If, during the roll-in/proficiency testing period of approximately 150 donations across three sites, there are:

Statistical Analysis Plan Version: 1.0 Date: 26-Apr-2020

• 1 or more severe hypotensive events [1.5 (Hypotensive; Severe (With or Without LOC)) or 1.6 (Hypotensive; Injury)] of the IQPP definition, as applied in the plasma center adverse event reporting system, reported to the sponsor,

Or if there are:

• 2 or more severe hypotensive events [1.5 (Hypotensive; Severe (With or Without LOC)) or 1.6 (Hypotensive; Injury)] of the IQPP definition, as applied in the plasma center adverse event reporting system, at any point in the first 10,000 donations, reported to the sponsor,

the DMC will be informed within 24 hours and will perform an unblinded review. The DMC should make a determination by the end of the next business day after the event was reported to the sponsor.

If the DMC determines relatedness and decides that the safety profile of the study should be reconsidered, the study is put on hold immediately. Information of the event and DMC's decision is transmitted to FDA immediately. The study is not resumed unless and until FDA has decided that it is safe to do so.

4. INTERIM ANALYSIS

One interim analyses may be conducted, when data from 16,000 apheresis procedures will be available. The interim analysis may result in sample size re-estimation of the sample size in accordance with the promising zone approach. It can be increased to include up to approximately 30,000 donations. Maximum 7,500 donors might be included.

Early termination of the trial due to safety concerns may be possible, when collected data at the interim analysis will provide strong evidence against establishment of non-inferiority at the end of the trial.

Statistical Analysis Plan Version: 1.0 Date: 26-Apr-2020

Should the formal interim analysis be conducted, the exact boundaries and decision rules will be finalized at least one week prior to interim analysis unblinding. The SAP will be amended to accommodate these additions.

5. SAMPLE SIZE CONSIDERATIONS

In order to evaluate the operating characteristics of the study design and the analysis methodology, extensive Monte-Carlo simulation study was conducted. The experiment was designed with an objective to mimic the real study as closely as possible (with assumptions presented in Appendix 3). The historic data on significant hypotensive AE rates, study population demographics, first-time donor status etc. was analyzed to inform the simulation study.

This experiment evaluated the relationship between number of subjects, number of donations and the probability of rejecting the null hypothesis for the various assumptions of the true AE rates. Type I error was evaluated for multiple scenarios when the true AE rate of the experimental arm was unacceptably large: $P_{Exper} - P_{Ctrl} > \delta$

NI margin δ is set at level of 0.0015 (0.15%). For the power analysis, 5,000 simulations were conducted and power was calculated as follows:

$$Power = \frac{N(reject H_0)}{N_{sim}} * 100\%$$

Power is calculated for rejecting H_0 at significance level of 2.5% (using 97.5% one-sided CI for the AE rate difference).

Statistical Analysis Plan Version: 1.0 Date: 26-Apr-2020

Incidence rate of AE in the experimental group is assumed to be 0.0015 (0.15%). The total sample size of 6,000 subjects (3,000 per group) with an expectation of 24,000 total donations yields acceptable profile of power and type I error.

In the scenario when the experimental procedure is at least as safe as the standard one there is greater than 85% power to establish the NI.

Type I error is below 2% for the scenario when $P_{Exper} - P_{Ctrl} = 0.00175$ and is as low as ~ 1% for

 $P_{Exper} - P_{Ctrl} = 0.0020.$

Performance of the estimation method during the simulations in terms of statistical power for detecting difference in levels of significant AE incidence rate in experimental versus control groups, given the δ =0.0015, in various scenarios is presented below in Table 1.

Table 1: Performance of estimation method using 24,000 plasmapheresis procedures.

PExper – PCtrl	≤0	0.0005	0.00075	0.0010	0.0015	0.00175	0.0020
Power	>85%	68.4%	49.4%	28.5%	5.7%	1.9%	1.1%

Statistical Analysis Plan Version: 1.0 Date: 26-Apr-2020

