3.1.1. STATISTICAL ANALYSIS METHOD

Given the nature of the data where donors contribute multiple data samples (donations), Generalized Estimation Equations Logistic Regression (GEE Logistic) framework for the repeat measures will be used (Halekoh, 2006; Yan J, 2004). The regression equation is presented below with Patient ID representing the random effect, and plasmapheresis method (study group) being fixed effect. Additional covariates are age, gender, BMI, and first-time donor status.

 $Logit(P(AE_{i,t}=1)) = \beta_0 + \beta_{Treatment} \times Treatment_i + \beta_{Age} \times Age_{i,t} + \beta_{Gender} \times Gender_i + \beta_{First \ Comer} \times First \ comer_{i,t} + \beta_{BMI} \times BMI_{i,t} + \varepsilon_{i,t},$

Corr(AE_{i,j}, AE_{i,k}) is exchangeable across all donors.

$$Corr(AE) = \begin{bmatrix} 1 & \gamma & \gamma & \gamma \\ \gamma & 1 & \gamma & \gamma \\ \gamma & \gamma & 1 & \gamma \\ \gamma & \gamma & \gamma & 1 \end{bmatrix}$$

Statistical Analysis Plan Version: 1.0 Date: 26-Apr-2020

AE represents the occurrence of a hypotensive AE (at least one), during the plasmapheresis procedure. *Treatment* is the variable representing plasmapheresis group (1=Experimental group, 0=Control group). For the *Gender* variable 1=Female, 0=Male. In *First comer* variable 1=First-time donor and 0=Repeat donor. First-time donors are those who have never undergone a plasmapheresis procedure. Age and BMI are continuous variables. i represents subject ID and t represents donation number for the given i subject.

Correlation structure within patients will be assumed to be exchangeable. Derivation of the final correlation model is currently in progress. The correlation structure can also be defined with the use of the historic data from the current study centers.

The above modeling will be used to obtain estimates of difference in proportions of significant hypotensive (vasovagal/hypovolemia) AE rates ($P_{Exper} - P_{Ctrl}$) in experimental and control groups along with its one-sided 97.5% upper limit of the CI calculated with Wald method.

[figure not shown]

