3.1.2. HYPOTHESIS TESTING

Non-inferiority (NI) hypothesis testing framework will be used in the primary analysis.

 $H_0: P_{Exper} - P_{Ctrl} \ge \delta$ $H_a: P_{Exper} - P_{Ctrl} < \delta$

Where δ is the NI margin and is defined to be 0.0015.

The hypotheses will be tested using comparison of the upper limit of the one-sided 97.5% Confidence Interval (CI) for the rate difference ($P_{Exper} - P_{Ctrl}$) to the non-inferiority (NI) margin δ . H_0 will be rejected and NI will be demonstrated if the above mentioned upper limit is less than the NI margin δ . Some hypothetical examples are presented in the Figure 1 below.

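### SAP section 5, Table 1 shows 5.7% rejection at exactly the non-inferiority margin against a stated one-sided level of 2.5%, and nothing in the plan reconciles the two

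*SAP*

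**What the plan says.** SAP 3.1.2 sets the margin at 0.0015 and defines the null hypothesis as an experimental-minus-control difference of 0.0015 or more, so the margin itself is a null value. The decision rule is that "H_0 will be rejected and NI will be demonstrated if the above mentioned upper limit is less than the NI margin". SAP 3.1.1 takes the difference from a GEE logistic model, "along with its one-sided 97.5% upper limit of the CI calculated with Wald method".

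SAP section 5 repeats the level: "Power is calculated for rejecting H_0 at significance level of 2.5% (using 97.5% one-sided CI for the AE rate difference". On false acceptance it says "Type I error was evaluated for multiple scenarios when the true AE rate of the experimental arm was unacceptably large", meaning differences strictly greater than the margin. The figures in the text are for such differences only: "Type I error is below 2% for the scenario when" the difference is 0.00175, and about 1% at 0.0020. It concludes that 6,000 subjects with an expected "24,000 total donations yields acceptable profile of power and type I error".

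Table 1 of section 5 gives, in a row labelled as power, 68.4%, 49.4%, 28.5%, 5.7%, 1.9% and 1.1% at differences of 0.0005, 0.00075, 0.0010, 0.0015, 0.00175 and 0.0020, and more than 85% at zero or below. Section 5 also assigns an event rate of 0.0015 to the experimental group.

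**The concern.** The entry at 0.0015 is a type I error, although the row is labelled power. It is the one column that shows whether a rule holds its nominal level at the boundary, and it is more than twice that level. The text does not mention it; it quotes only the two columns further out, where rejection is bound to be lower, and calls the profile acceptable.

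This is the primary safety test. If the simulation applied the planned rule, a collection procedure with exactly the excess event rate that the plan treats as unacceptable would pass more often than the plan states. If the simulation applied something else, the margin column does not describe the planned test, and the entries at 0.0005 to 0.0010 may not either.

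**Working it through.** **Inputs.** Margin 0.0015 and null hypothesis: SAP 3.1.2. One-sided 97.5% Wald limit: SAP 3.1.1 and section 5. 24,000 donations, 1:1, taken as 12,000 per arm; 5,000 runs; event rate 0.0015: section 5. Assumption: 0.0015 is used as the control rate, and donations are treated as independent.

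**1. The plan's own power figure.** At zero difference with 0.0015 in both arms, SE = √(2 × 0.0015 × 0.9985 / 12,000) = 0.000500. Power = Φ(0.0015 / 0.000500 − 1.960) = Φ(1.04) = 85.1%. Exact enumeration of the two binomials with the Wald limit gives 85.0%. The headline of about 85% reproduces at the 2.5% level.

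**2. The same rule at the margin.** The normal approximation gives Φ(0 − 1.960) = 2.5%, whatever the SE. Exact enumeration, with rates 0.0015 and 0.0030, gives 2.9%. Varying the control rate from 0.0005 to 0.003 moves the exact value only between 3.8% and 2.7%. Small-count error in the Wald limit is therefore worth about 0.2 to 1.3 points, against a gap of 5.7 − 2.5 = 3.2 points.

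**3. Monte Carlo error.** If the true rate were 2.5%, SE = √(0.025 × 0.975 / 5,000) = 0.22 points, and 3.2 points is 14.5 such errors. 5.7% of 5,000 is 285 runs; the exact 95% interval is 5.07% to 6.38%.

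**4. Does a simple alternative explain the table?** Exact binomial Wald, independent donations, per cent rejecting:

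| True difference | SAP Table 1 | Control 0.0015, 97.5% limit | Control 0.0015, 95% limit | Experimental fixed at 0.0015, 97.5% limit |
|---|---|---|---|---|
| 0 | >85 | 85.0 | 91.0 | 85.0 |
| 0.0005 | 68.4 | 46.5 | 58.4 | 60.4 |
| 0.00075 | 49.4 | 28.0 | 38.8 | 43.9 |
| 0.0010 | 28.5 | 14.7 | 22.6 | 27.2 |
| 0.0015 | 5.7 | 2.9 | 5.4 | 5.5 |
| 0.00175 | 1.9 | 1.1 | 2.3 | undefined |
| 0.0020 | 1.1 | 0.4 | 0.9 | undefined |

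Two readings come close to 5.7% at the margin: a 95% one-sided limit, and an experimental rate held at 0.0015. Neither fits every column. The last one cannot have produced the whole table: the control rate would be 0.0015 − 0.0015 = 0 at the margin, and −0.00025 and −0.0005 in the next two columns. These columns test explanations; they are not forecasts of the corrected power.

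**The case against.** The 5.7% is printed openly, and section 5 says plainly that type I error was looked at beyond the margin. That is true, but the stated level applies to the whole null hypothesis, which includes the margin.

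The independence check does not replicate the SAP's simulation. Appendix 2 generates correlated binary events (0.1 with the first donation, 0.5 between repeat donations) and stops a donor after an event. This reservation stands, and it is why the cause stays open. Rough clustered simulations, without covariates and not using the Appendix 2 generator exactly, gave about 3% to 4.5% at the margin when the realised difference stayed near 0.0015. When stopping combined with correlation pulled the realised difference down to 0.0013, rejection was 6.2%, and it was higher still with stronger correlation. Appendix 2, Table 4 reports a realised difference of 0.001518541, slightly above the margin, which does not favour that second route but does not exclude it.

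The sentence assigning 0.0015 to the experimental group can be read as describing only the zero-difference scenario, where it fits. It then needs clarifying; it is not necessarily wrong.

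SAP 3.1.1 also says the final correlation model is still being derived, so Table 1 may be provisional, and a figure beside the Wald sentence is not visible in the text available here, so a formula there cannot be ruled out. On the table's own values the practical looseness is small: log-linear interpolation between 5.7% and 1.9% reaches 2.5% at about 0.0015 + 0.00025 × ln(5.7/2.5) / ln(5.7/1.9) = 0.00169, roughly 0.0002 beyond the margin.

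**Conclusion.** The discrepancy is real: 5.7% (interval 5.1% to 6.4%) at a null value, against a stated 2.5%. That rests only on SAP 3.1.2 and section 5. That small counts do not account for it rests on the independence check (about 2.9%). Either the planned rule is oversized at the margin, or Table 1 used a different limit or different rates.

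A reader might infer more, and the documents do not support it:

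- That the planned test has been shown to run at 5.7%. Table 1 may not have been produced with the planned rule.
- That a 95% limit was used by mistake. It fits the margin column but misses the entries at 0.0005 to 0.0010.
- That the trial is underpowered. Power of about 85% at zero difference reproduces at the stated level, so this point alone does not call for more donations.

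The point should be fixed because it concerns the error rate of the primary safety test. It does not affect trial conduct.

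**What to change.** - State the confidence level and the event rates in both arms that were simulated for each Table 1 column, and say to which scenario the 0.0015 experimental rate applies.
- State in SAP 3.1.1 how the rate difference and its Wald limit are derived from the logit GEE, and use the same derivation in the simulation.
- Re-run Table 1 under the planned 97.5% rule with the Appendix 2 correlation and stopping assumptions. Correct the table, and report type I error at exactly 0.0015 in the text.
- If the planned rule still clearly exceeds 2.5% at the margin, either restate the type I error or adjust the limit and restate power under it.

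The cost is SAP wording and a simulation re-run. Some stated figures may become less favourable; how far cannot be said before the re-run.

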# 1. Introduction and Background

## 1.1 Executive Summary

This is a multicenter, randomized, prospective IDE clinical trial to evaluate the safety and effectiveness of the NexSys® Plasma Collection System utilizing a Percent Plasma Nomogram (PPN) feature for plasmapheresis. The clinical trial is designed to collect approximately 24,000 plasmapheresis procedures from around 5,000 - 6,000 donors. Donors will be randomized 1:1 to the experimental group undergoing plasmapheresis using NexSys® PCS with the PPN feature vs. the control group undergoing plasmapheresis NexSys® PCS with YES® technology. As repeat donations by the same donor are expected, the donor will remain in the same study group during the entire course of the clinical trial. In an effort to prevent bias, the clinical trial will be blinded to select members of the sponsor study team in accordance with the blinding plan, and subjects will not be actively made aware to which group they have been randomized – however, subjects may be able to determine to which group they have been assigned. The sample size of the clinical trial can be reevaluated based on the number of donations and observed significant hypotensive (vasovagal/hypovolemia) events according to the plasma center adverse event reporting system, based on the IQPP definitions.

In the United States, the demand for plasma has increased four-fold over the past twelve years and is expected to continue rising. The US Source Plasma Collectors will struggle to meet this demand. The FDA plasma collection nomogram published by the Center for Biologics Evaluation and Research (CBER) in 1992 has been used by source plasma collectors for the past 25 years. Field experience has demonstrated that the 1992 FDA nomogram is safe for donors, with a rate of significant hypotensive (vasovagal/hypovolemia) adverse events of approximately 0.15% according to the plasma center adverse event reporting system, based on the IQPP definitions.

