The variable *First comer* is generated from Binomial distribution with the mean parameter μ_{first} *comer* = 0.146:

First comer ~ $B(\mu first comer)$

Where *First comer* = 1 for first comers, *First comer* = 0 for repeat donors.

GENERATION OF ADVERSE EVENTS

AEs for the patients are generated using the method of Emrich and Piedmonte for correlated binary data.

The corresponding function for generating AEs uses the mean vector *Mean AE*, and the correlation matrix *Corr AE* to generate AEs for the patients. Correlation between first donation and other donations within a patient is assumed to be 0.1, while the correlation between repeat donations is assumed to be 0.5.

For example, correlation matrix Corr AE for a patient with 4 donations is:

$$Corr \ AE = \begin{bmatrix} 1 \ 0.1 \ 0.1 \ 0.1 \ 0.1 \\ 0.1 \ 1 \ 0.5 \ 0.5 \\ 0.1 \ 0.5 \ 1 \ 0.5 \\ 0.1 \ 0.5 \ 0.5 \ 1 \end{bmatrix}$$

Average rates of AEs for the age groups are presented in the Table 3.

Table 3: Adverse event distributions by age groups of patients.

Age	18-20	21-24	25-44	45-64	65+
AE rates	0.004579	0.002165	0.0011	0.000827	0.000951

Statistical Analysis Plan Version: 1.0 Date: 26-Apr-2020

The mean vector *Mean AE* for a patient with 4 donations includes 4 values, which can be found using the following equation:

 $Mean AE = \beta_{Age} * Age + \beta_{Gender} * Gender + \beta_{Method} * Method + \beta_{First Comer,Female} *$ $(First Comer, Female) + \beta_{First Comer,Male} * (First Comer, Male)$

Where coefficient β_{Age} takes the five values of AE rates described in Table 2. Average AE rate is 0.003831 for females, and 0.001145 for males, so $\beta_{Gender} = 0.003831 - 0.001145 = 0.002686$. The study also demonstrates that average AE rate is 0.01302 for female first comers, compared to 0.002098 for female repeat donors, thus $\beta_{First \ comer,Female} = 0.01302 - 0.002098 = 0.010922$. Average AE rate is 0.003061 for male first comers, compared to 0.002581.

Additionally, we assume that donors stop the plasmapheresis after having an AE.

Table 4: *Comparison of variable values in the population data and theoretical targets/historical estimates.*

Variable name	Population data 0 difference of AEs between arms	Population data 0.0015 difference of AEs between arms	Target / historical estimate
Difference of AEs between arms	0.000001228461	0.001518541	0/0.0015

Statistical Analysis Plan Version: 1.0 Date: 26-Apr-2020

Proportion of females	0.3570712	0.3578287	0.357

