Average weight in lbs	213.7896	214.1136	211.2
Average height in inches	68.76917	68.75169	68.76
Proportion of people with age 18-20	0.06798374	0.06786572	0.0669
Proportion of people with age 21-24	0.1494797	0.1505201	0.1512
Proportion of people with age 25-44	0.5237046	0.5253826	0.5235
Proportion of people with age 45-64	0.2533512	0.2502998	0.2530
Proportion of people with age 65 and above	0.00548081	0.005931791	0.0054
Proportion of donors in experimental arm	0.4989608	0.4954739	0.5
Number of donations per patient	4.055597	4.04431	4
Proportion of first comers	0.14677	0.14501	0.146
AE rates for age group 18-20	0.003010082	0.003825555	0.004579
AE rates for age group 21-24	0.001789587	0.002595483	0.002165
AE rates for age group 25-44	0.00134408	0.002127249	0.0011
AE rates for age group 45-64	0.001201847	0.001669482	0.000827
AE rates for age group 65 and above	0.0002249213	0.002084202	0.000951
β_{Gender}	0.001733372	0.001720488	0.002686
$eta_{First\ comer,Female}$	0.01431423	0.01592894	0.010922
$eta_{First\ comer,Male}$	0.003890562	0.003096266	0.002581

Protocol No: TP-CLN-100467(AB)

Page 34 of 34

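### SAP 5 assigns the 0.15% planning rate to the experimental arm, which Table 1 cannot accommodate; separately, Table 1's power at small excess risks (68.4/49.4/28.5%) does not follow from the stated inputs

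*SAP*

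**What the plan says.** SAP section 5 gives one base rate for the simulation: "Incidence rate of AE in the experimental group is assumed to be 0.0015 (0.15"%). It gives the margin as "NI margin δ is set at level of 0.0015 (0.15"%) and the test level as "Power is calculated for rejecting H_0 at significance level of 2.5% (using 97.5% one-sided CI for the AE rate difference"). SAP 3.1.1 specifies the "one-sided 97.5% upper limit of the CI calculated with Wald method". The planned size is 6,000 donors, 3,000 per group, with 24,000 donations expected.

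Table 1 in section 5 reports these rejection rates, from 5,000 simulations:

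| Difference (experimental − control) | ≤0 | 0.0005 | 0.00075 | 0.0010 | 0.0015 | 0.00175 | 0.0020 |
|---|---|---|---|---|---|---|---|
| Stated | >85% | 68.4% | 49.4% | 28.5% | 5.7% | 1.9% | 1.1% |

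Three other places bear on which arm carries the 0.15%:

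- Protocol 1.1 describes field experience with the 1992 FDA nomogram "with a rate of significant hypotensive (vasovagal/hypovolemia) adverse events of approximately 0.15"%.
- SAP 5 describes the type I error scenarios as those where "the true AE rate of the experimental arm was unacceptably large".
- SAP Appendix 2, Table 4 has a column headed "Population data 0.0015 difference of AEs between arms", with realised rates by age group (for example the row "AE rates for age group 25-44").

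**The concern.** There are two faults, and they should be kept apart.

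First, the base-rate sentence and Table 1 cannot both be true. The 0.15% is the historical rate under the existing nomogram, so it describes the control arm. Placed in the experimental arm, it makes the two right-hand columns of Table 1 impossible. Those are the columns on which section 5 rests its statements that type I error is below 2% and about 1%.

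Second, the power entries at small positive differences look too high for the stated rate, size and test. These columns show how the trial behaves if the new nomogram carries a modest excess risk. Protocol 2.2 allows for a marginal rise in some donors, and Protocol 10.2 allows that the rate in the trial population may rise. Table 1 is also the only power profile in the plan, while the interim re-estimation boundaries in SAP 4 are still to be written. A reader would take the trial to have about two chances in three at an excess of 0.05 percentage points. On the stated inputs it has fewer than one in two.

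**Working it through.** **Inputs.** Margin 0.0015, one-sided 2.5% and 24,000 donations (SAP 5); Wald limit (SAP 3.1.1); 1:1 allocation (SAP 1.2.3), so n = 12,000 donations per arm; base rate 0.0015 (SAP 5, Protocol 1.1).

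**Step 1: the sentence against Table 1.** If the experimental rate is 0.0015, the control rate is 0.0015 − d:

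- d = 0.0005, 0.00075, 0.0010: control 0.0010, 0.00075, 0.0005
- d = 0.0015: control 0
- d = 0.00175: control −0.00025
- d = 0.0020: control −0.0005

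The last two cannot exist.

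**Step 2: what Appendix 2 simulated.** Table 4's age-specific rates are weighted by Table 4's age shares.

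- Zero-difference population: overall rate 0.00148.
- 0.0015-difference population: 0.000260 + 0.000391 + 0.001118 + 0.000418 + 0.000012 ≈ 0.00220.

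The second is split using that column's experimental share (0.4955) and realised difference (0.001519):

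- control = 0.002198 − 0.4955 × 0.001519 ≈ 0.00145
- experimental ≈ 0.00145 + 0.00152 ≈ 0.00296

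This treats donor shares as donation shares, which is close enough here. The base rate sits in control and the excess was added to the experimental arm.

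**Step 3: reproduce the stated power at no difference.** Power = Φ((0.0015 − d)/SE − 1.96), with SE = √[p_C(1 − p_C)/n + p_E(1 − p_E)/n].

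At d = 0, SE = √(2 × 0.0015 × 0.9985/12,000) = 0.000500, so power = Φ(3.002 − 1.960) = 85.1%. Exact enumeration of the binomial Wald rule gives 85.0%. The stated figure reproduces.

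**Step 4: the same rule at positive differences, control 0.15%.**

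- d = 0.0005: SE 0.000540, Φ(1.853 − 1.960) = 45.8%
- d = 0.00075: SE 0.000558, Φ(1.343 − 1.960) = 26.9%
- d = 0.0010: SE 0.000577, Φ(0.867 − 1.960) = 13.7%

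Exact enumeration, with the literal reading alongside:

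| d | Stated | Control 0.15%, exact | Stated minus exact | Experimental 0.15%, exact |
|---|---|---|---|---|
| 0.0005 | 68.4% | 46.5% | 21.9 | 60.4% |
| 0.00075 | 49.4% | 28.0% | 21.4 | 43.9% |
| 0.0010 | 28.5% | 14.7% | 13.8 | 27.2% |
| 0.0015 | 5.7% | 2.9% | 2.8 | 5.5% |
| 0.00175 | 1.9% | 1.1% | 0.8 | undefined |
| 0.0020 | 1.1% | 0.4% | 0.7 | undefined |

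Monte Carlo error for 5,000 runs is at most 2 × √(0.5 × 0.5/5,000) = 1.4 points, so chance does not explain the three middle gaps.

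**Step 5: does clustering explain it?** A donor-level simulation was run with Appendix 2's correlations (0.1 and 0.5) and stopping after an event, calibrated to a realised control rate of about 0.15% (1,200 runs). It gave 85.4%, 49.2%, 30.8% and 14.9% at d = 0, 0.0005, 0.00075 and 0.0010, so the gap remains. Two other settings also failed to match Table 1 (600 runs each):

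- Correlation without stopping: 54% at d = 0, which contradicts the stated figure above 85%.
- The 0.15% and d taken as rates before stopping: about 81%, 65% and 54% at the three middle differences. The realised control rate is then about 0.095%, which also conflicts with Table 4.

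**Step 6: other settings.** Control at 0.10% with one-sided alpha 0.05 gives 70.6%, 47.9%, 27.5%, 5.8%, 2.2% and 0.7% (exact). That is within about 2.5 points of every entry above zero. No variant tried brought all three middle entries within 2 points.

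**The case against.** The strongest reply is that the sentence is a wording slip with no consequence. Table 4 shows that the 0.0015 population kept the base rate in control, so negative rates were never simulated. Sample size rests on the no-difference case, which reproduces. Margin, hypothesis and decision rule are untouched. All of that stands.

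A reader might infer that the misplaced arm produced the high power entries, because the literal reading moves in their direction. The documents do not support this. With experimental at 0.15% the results are 60.4% and 43.9%, still 8.0 and 5.5 points below the table at the first two differences, and Table 4 points the other way. A different alpha or base rate in the simulation is possible, but nothing in the documents establishes it.

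It is also fair that Table 1 comes from a covariate-adjusted GEE with correlated donations, whereas the exact figures use unadjusted independent binomials. Arm rates for the middle columns are not given. Appendix 2's input rates by gender average to about 0.21% (0.357 × 0.003831 + 0.643 × 0.001145), against about 0.14% from its input rates by age. A higher control rate would lower power further. So 46/28/15% are reference values, not established replacements.

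Finally, an excess of 0.0005 is a one-third relative rise (0.0005/0.0015) across the whole arm, and 0.0010 is two-thirds. Protocol 2.2 expects overall risk to be held constant. These columns are plausible stress cases rather than the planning case, which bears on severity but not on whether the figures are right.

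**Conclusion.** SAP 5 is wrong as written and should be corrected. The base-rate sentence is incompatible with Table 1 and with Protocol 1.1 and Appendix 2, which imply a control rate of about 0.145% to 0.15%.

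Separately, Table 1's power at 0.0005, 0.00075 and 0.0010 is not reproduced. On the stated inputs it is about 46%, 28% and 15%, some 14 to 22 points lower. This assumes a control rate of 0.15%, 12,000 close-to-independent donations per arm and the one-sided 97.5% Wald rule. The calibrated clustered simulation gives a similar picture. The cause of the gap cannot be determined from the documents.

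Two stronger conclusions might be drawn, and neither is supported. One is that the trial is too small: the no-difference power of about 85% reproduces, and that is the case on which the size was chosen. The other is that the planned test has an inflated error rate, because Table 1 shows 5.7% at the margin. With control at 0.15% the exact Wald figure there is 2.9%, so the 5.7% is a further sign that the simulation settings need checking, not proof of a fault in the test.

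**What to change.** In SAP 5, state that the control-group rate is 0.0015 and the experimental-group rate is 0.0015 plus the difference shown. Re-run Table 1 with the final estimator at one-sided 2.5%, using Appendix 2's correlation and stopping assumptions. Print both arms' realised rates under each column and confirm the alpha used. Replace the power entries with the re-run values, which should fall near 46%, 28% and 15% if events are close to independent. Keep the sample size.

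The cost is one simulation run and an SAP edit. The downside is that the stated power at small positive differences becomes less favourable. Correcting the sentence without the re-run would leave the table unexplained.
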